8.3.3 Sputum Rheology

Sputum for the determination of rheological properties will be collected at visits 2, 5, and 8. The rheological measurements may be made using a portion of the sample collected at this time.

9 EVALUATIONS BY VISIT

9.1 Visit 1

- 1. Review the study with the participant and obtain written informed consent and HIPAA authorization.
- 2. Assign the participant a unique screening number.
- 3. Record demographics data.
- 4. Record medical history, including history of asthma, diagnosis date, and asthmarelated healthcare utilization & exacerbation frequency.
- 5. Record concomitant medications.
- 6. Perform a complete physical examination.
- 7. Perform and record vital signs.
- 8. Perform and record oximetry.
- 9. Perform and record urine pregnancy test.
- 10. Perform and record spirometry.
- 11. Schedule participant for Visit 2 in 7 days.

9.2 Visit 2a

- 1. Concomitant medications review.
- 2. Perform and record vital signs.
- 3. Perform and record oximetry.
- 4. Perform and record urine pregnancy test.
- 5. Perform and record spirometry.
- 6. Perform and record post-bronchodilator spirometry.
- 7. Collect blood for clinical laboratory tests.
- 8. Obtain a CT scan of the thorax.
- 9. Collect induced sputum.
- 10. Schedule participant for Visit 3.

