1.1 Overview of Clinical Studies

Against this background, the preliminary data we show in Figs 1 and 2 are very important, because we show how CT lung images can reveal mucus plugs in chronic severe asthma and how these plugs are associated with lower lung function. Specifically, we use CT imaging to uncover that a majority (58%) of asthmatics in the NHLBI Severe Asthma Research Program (SARP) have at least one lung segment with a mucus plug and 27% have more than four lung segments with mucus plugs. Notably, asthmatics with a high mucus scores achieve a post albuterol FEV1 > 80% much less frequently than asthmatics who have a zero mucus score (Fig 3).

Examined another way, we find that all asthmatics with an FEV1 \leq 60% after

[figure not shown]

Figure 2. A. The CT mucus segment score is usually 0 in health but many asthmatics enrolled in the NHLBI Severe Asthma Research Program have scores above 0 with some as high as 15-19. B. The frequency distribution of mucus score in asthma shows that 42% of patients have a score of 0 (zero mucus score); among the remaining 58% of asthmatics, the median mucus score was 3.5, and we classified score between 0.5 and 3.5 as "low" and above 4.0 as "high".

albuterol treatment have abnormal mucus scores, whereas the majority of asthmatics with an FEV1 >80% with albuterol treatment have zero or low mucus scores (Fig 3). These data clearly implicate mucus plugs in the pathogenesis of airflow obstruction in asthma. One reason why this role for mucus plugging has been underappreciated in chronic severe asthma is that mucus-related symptoms are both insensitive and non-specific indicators of mucus. This is well illustrated in the table, which presents data for the prevalence of mucus-related symptoms in asthmatics with different mucus score categories. None of the mucus-related symptoms were significantly different in the zero, low or high mucus subgroups, and it is clear that these symptoms have very limited utility to investigate the

role of mucus in asthma or to identify asthmatics who might benefit from mucus-directed treatments.

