6.2 Inclusion Criteria

- 1. Male or female between the ages of 18 and 70 years of age at Visit 0.
- 2. Able to perform reproducible spirometry according to ATS criteria
- 3. Clinical history consistent with moderate to severe asthma for 1 year or greater.
- 4. Post-bronchodilator FEV1 <90% of predicted
- 5. Prescription and daily use of inhaled corticosteroid (ICS) equivalent to 80mcg of beclomethasone or greater
- 6. CT mucus score >3 (determined during the initial screening process, provided the prior two conditions are met)
- 7. Written informed consent obtained from participant and ability for participant to comply with the requirements of the study.

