8.1.12 Sputum Induction

A 12 minute sputum induction using 3% hypertonic saline will be performed at visits 2, 5, and 8. The procedure will be carried out according to the UCSF Airway Clinical Research Center Sputum Induction Manual of Procedures (Appendix C).

Associated risks include the following:

- Likely (>25%)
 - · Salty after taste in the mouth, coughing, or a feeling of needing to swallow.
- Less Likely (<5%)
 - Sore throat, shortness of breath, wheezing, chest tightness, light-headedness, nausea, or headache.
 - · Worsening of lung function.
- Rare but serious (<1%)
 - Some patients have had a severe asthma attack or a reaction to the salty water that they breathe in.

In an effort to minimize risk to participants, bronchodilator treatment will be available if sputum induction induces a worsening of asthma symptoms. The following safety procedures will be followed for the sputum induction procedure; only participants with a post-bronchodilator FEV1 of >50% predicted will undergo sputum induction, a physician will be available during the induction; study staff will calculate and record the peak flow and FEV1 value that equals both a 10% and 20% fall in lung function based upon the recorded post-bronchodilator peak flow and FEV1 values and participants will not be discharged until their FEV1 is within 10% of their post-bronchodilator FEV1.

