8.1.14 CT Imaging of the Thorax

A single inspiratory low dose CT scan of the thorax using a model based iterative reconstruction (MBIR) approach will be taken at baseline (visit 2) and following both treatment periods (visits 5 and 8).

The risks associated with CT scanning are that of the additional amount of radiation exposure. The additional amount of radiation that each participant will receive as a result of participating in this study will be approximately 4 mSv, which is slightly greater than the yearly natural background of radiation in the US, which is 3mSv. This amount of radiation may involve a low risk of cancer. A participant should not participate in this study if she is pregnant or breastfeeding.

Additional risks are associated with the uncovering abnormal findings. There is a risk of possible detection of an abnormality in the lung which, after testing or treatment, is found not to be disease-causing. This includes possible misdiagnosis of lung cancer. Such

Version #:1.5 Version Date: 8/5/2016 Page 24 of 41

findings may result in unnecessary anxiety for the participant, and increase his or her chance that an outpatient physician may believe that the abnormality is lung cancer and order further testing. This testing could include additional CT scans with additional radiation exposure, other types of scans to determine if the abnormalities are rapidly growing, a needle biopsy (taking a sample of the abnormality with a needle) or a lung biopsy which requires surgery. Whether these additional studies would be performed would be a decision that the participant would make with his/her regular physician.

In an effort to minimize risk to participants, scans will be read by radiologists that have expertise in interpreting findings of chest CTs. If there are any abnormalities, other than those that are usually found in asthmatic patients, observed by the clinical center radiologists, these will be reported to the principal investigator, who will in turn communicate these findings to the participant. The most likely abnormal result will be the identification of a spot on the lung that might be cancer.

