8.3 Research Laboratory Measurements

8.3.1 Sputum Cell Count and Differential

Sputum for determination of total and differential cell counts will be collected at visits 2, 5, and 8. Specimens will be collected and processed according to the UCSF Airway Clinical Research Center Sputum Induction Manual of Procedures (Appendix C).

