8.2.1 Visit 2b **Optional

- 1. Perform and record vital signs.
- 2. Perform and record oximetry.
- 3. Perform and record urine pregnancy test.

Version #:1.5 Version Date: 8/5/2016 Page 26 of 41

- 4. Perform and record spirometry.
- 5. Perform methacholine challenge testing.
- 6. Collect blood for clinical laboratory tests.
- 7. Obtain a CT scan of the thorax.
- 8. Collect induced sputum.
- 9. Schedule participant for Visit 3.

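### Visit 2 induces sputum before the qualifying CT score is read, so people who then fail the CT criterion undergo an induction with no planned use

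*Combined protocol and SAP*

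**What the plan says.** Eligibility requires "Post-bronchodilator FEV1 <90% of predicted" and daily inhaled corticosteroid (section 6.2, criteria 4 and 5). Criterion 6 then asks for "CT mucus score >3 (determined during the initial screening process, provided the prior two conditions are met".

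Section 8.1.14 says that the CT scans "will be taken at baseline (visit 2) and following both treatment periods (visits 5 and 8". The Visit 2a list (section 9.2) gives post-bronchodilator spirometry, blood, CT, then "9. Collect induced sputum", then the booking of Visit 3. The optional Visit 2b list, for people who need methacholine testing, has CT followed by "8. Collect induced sputum". A footnote to the schedule of events confirms that blood, CT and sputum are each taken at one of these two visits.

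Section 8.3.1 states: "Sputum for determination of total and differential cell counts will be collected at visits 2, 5, and 8". Sections 8.1.12, 8.3.2 and 8.3.3 name the same visits. Section 8.1.12 limits induction to people with post-bronchodilator FEV1 above 50% predicted. It lists wheeze, chest tightness and worsening lung function among effects expected in under 5%. Under the rare but serious heading (under 1%) it says: "Some patients have had a severe asthma attack or a reaction to the salty water that they breathe in".

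**The concern.** The protocol already screens in steps: the CT criterion is considered only if the FEV1 and corticosteroid criteria are met, and methacholine is reserved for those who need it. Induction has a safety floor but no eligibility condition, although the result that decides eligibility comes from a scan taken just before it at the same visit.

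The uses of sputum named in section 14.4 are baseline elasticity (G') as a predictor of response to NAC, and the effect of treatment on G'. Both need treated participants. Someone who fails the CT criterion therefore carries the risk of the procedure, in moderate to severe asthma, for a sample with no stated purpose. Processing those samples for cell counts, RNA and rheology is also wasted effort.

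**Working it through.** **Order of steps.** Both Visit 2 lists go from CT to induction with no scoring step, eligibility check or hold. Nothing in the text lets an earlier CT qualify a person. That the score is unknown at induction is an inference from these lists, not a statement in the protocol.

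**Number to enrol.** The target is 30 (section 14.6). With SD 19, difference 10 and two-sided alpha 0.05, the paired normal formula gives (19 × (1.960 + 0.842) / 10)² = 28.3, so 29. Paired t power at 30 is 79.6%. The stated 30 is reproduced closely enough, and only this target enters below. The protocol gives no screen-failure rate and no number to be screened.

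**Pass share in the unselected cohort.** Section 1.1 reports that 42% score 0 and that "among the remaining 58% of asthmatics, the median mucus score was 3.5". The score bands there imply half-point steps, so 3.5 qualifies under >3. At least half of the 58% therefore pass: 0.5 × 0.58 = 0.29. The failure share is at most about 1 − 0.29 = 0.71. The other figure in that section, 27% with more than four plugged segments, would give 0.73. It is a stricter cut than >3, so 0.29 is the better floor.

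**Effect of the FEV1 criterion.** Section 1.1 links lower FEV1 to higher scores, so selecting on FEV1 below 90% raises the pass share. The amount is not given. Two assumed cases show the range:

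- Everyone scanned has a non-zero score: pass share 0.29 / 0.58 = 0.50.
- A share q of such a cohort has FEV1 below 90%, and every person scoring above 3 is among them. This is the most favourable case for a given q, with pass share 0.29 / q. The protocol does not give q.

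With pass share p, 30/p people are scanned and 30/p − 30 inductions are unneeded, if everyone scanned is induced:

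| Case | p | Failing | Scanned | Unneeded |
|---|---|---|---|---|
| Unselected cohort | 0.29 | 71% | 103.4 | 73.4 |
| q = 0.8 | 0.3625 | 64% | 82.8 | 52.8 |
| All scores non-zero | 0.50 | 50% | 60 | 30 |
| q = 0.5 | 0.58 | 42% | 51.7 | 21.7 |
| q = 0.4 | 0.725 | 28% | 41.4 | 11.4 |

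With every qualifier passing the FEV1 filter, the failure share stays at one half or more only if q is at least 0.29 / 0.5 = 0.58.

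**Replacements.** Section 7.5 allows kits for up to 8 replacements. Enrolling 38 multiplies the counts by 38/30 = 1.27, for example 38/0.29 − 38 = 93 and 38/0.50 − 38 = 38.

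**Risk ceilings.** At the upper limits in section 8.1.12, each effect in the under-5% group would occur in at most 0.05 × 73.4 = 3.7 people, or 0.05 × 11.4 = 0.6. The under-1% line gives at most 0.01 × 73.4 = 0.7, or 0.01 × 11.4 = 0.1. These are ceilings and not expected counts.

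**The case against.** Three stronger readings are tempting, and the documents do not support them.

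- A reader might infer that everyone screened is induced. Criterion 6 comes into play only after the FEV1 and corticosteroid criteria, and people with post-bronchodilator FEV1 of 50% predicted or less are not induced.
- A reader might infer that the protocol's own figures put half to two-thirds or more of inductions in ineligible people. Section 1.1 describes a cohort without this trial's FEV1 filter. Under strong enrichment the share falls below half.
- A reader might count the under-1% line as severe attacks. It also covers other reactions to the saline, and section 8.1.12 provides safeguards: a bronchodilator and a physician available, calculated limits for a fall in lung function, and a recovery condition before discharge.

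It can also be said that the visit lists are not complete decision rules. They omit the FEV1 conditions too, and the full schedule table and the sputum induction manual are not in the text available here. This stands as a caution. The surviving schedule footnotes show no CT condition, and no section states one.

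Moving the induction has costs. The medication holds in section 8.1.2 apply at Visits 2, 5 and 8, which are also the sputum visits. A baseline sample taken without them would differ in conditions from the later samples. Baseline CT and sputum would no longer share a day. These points stand and shape the fix. They do not remove the case for reading the score first.

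**Conclusion.** The point holds in a limited form. As written, sputum is induced at the same visit as the qualifying CT with no step to read the score, so some people who cannot enter the trial undergo a procedure whose sample has no planned use in section 14.4. Section 14 promises a later, detailed analysis plan that could add a use, but none is stated now.

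The number is uncertain: about 73 unneeded inductions to enrol 30 at the unselected pass rate, about 30 if every scanned person has a non-zero score, and 11 to 12 if only 40% of such a cohort has FEV1 below 90% and all qualifiers are among them. The counts assume that all scanned people are induced and ignore run-in losses. The FEV1 floor for induction would lower the counts. It could raise the failing share among those induced, because people with very low FEV1 all have non-zero scores in section 1.1.

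The primary endpoint, power and error rate are not affected. This is a modest improvement in participant safety and cost, worth making because even a dozen such inductions can be avoided.

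**What to change.** Make baseline sputum conditional on a confirmed CT mucus score above 3, and collect it after scoring and before the first run-in saline dose. Visit 3 is one suitable place: section 9.3 already lists post-bronchodilator spirometry, which the limits in section 8.1.12 need, ahead of the supervised run-in dose. The visit lists fix no interval between Visits 2 and 3, and the synopsis allows up to 90 days of screening, so there is time to score the scan. A separate slot after scoring would serve equally well.

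Consequential edits:

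- Remove induction from the Visit 2a and 2b lists, add it to the chosen visit, and update sections 8.1.3, 8.1.12 and 8.3.1 to 8.3.3 and the schedule of events.
- State whether the food and medication holds used at Visits 5 and 8 also apply at the new baseline sputum visit, so that within-person comparisons stay like for like.
- Reconcile section 9.7, which lists induced sputum at Visit 7, with the sections that name only Visits 2, 5 and 8.
- State the expected CT pass rate among people who meet the FEV1 criterion, if the sponsor has it.

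The cost is a protocol amendment, a longer Visit 3 for those who qualify, baseline CT and sputum on different days, and induction on the first run-in day. Fewer samples would need processing.

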8.2.1 Visit 2b **Optional

- 1. Perform and record vital signs.
- 2. Perform and record oximetry.
- 3. Perform and record urine pregnancy test.

Version #:1.5 Version Date: 8/5/2016 Page 26 of 41

- 4. Perform and record spirometry.
- 5. Perform methacholine challenge testing.
- 6. Collect blood for clinical laboratory tests.
- 7. Obtain a CT scan of the thorax.
- 8. Collect induced sputum.
- 9. Schedule participant for Visit 3.

9.3 Visit 3 (Day 0)

- 1. Record changes to concomitant medications.
- 2. Perform abbreviated physical examination.
- 3. Perform and record vital signs.
- 4. Perform and record oximetry.
- 5. Perform and record urine pregnancy test.
- 6. Perform and record spirometry.
- 7. Perform and record post-bronchodilator spirometry.
- 8. Provide education on use of personal nebulizer and administration of study medication.
- 9. Dispense study drug and initiate study diary.
- 10. Perform RN/MD supervised administration of first run-in dose of nebulized 0.9% normal saline.
- 11. Schedule participant for Visit 4 in 5 days.

9.4 Visit 4 (Day 5)

- 1. Record any adverse experiences and/or review participant diary for adverse experiences and exclusionary medication use.
- 2. Record changes to concomitant medications.
- 3. Perform abbreviated physical examination.
- 4. Perform and record vital signs.
- 5. Perform and record oximetry.
- 6. Perform and record urine pregnancy test.
- 7. Perform and record spirometry.
- 8. Perform and record post-bronchodilator spirometry.
- 9. Collect any unused study drug.
- 10. Review diary card.
- 11. Randomize if adherence is greater than or equal to 80% during run-in.
- 12. Provide education on use of personal nebulizer and administration of study medication.
- 13. Dispense study drug and initiate study diary.
- 14. Perform RN/MD supervised administration of first dose of nebulized study drug.
- 15. Schedule participant for Visit 5 in 7 days.

Version #:1.5 Version Date: 8/5/2016 Page 27 of 41

9.5 Visit 5 (Day 14)

- 1. Record any adverse experiences and/or review participant diary for adverse experiences and exclusionary medication use.
- 2. Record changes to concomitant medications.
- 3. Perform abbreviated physical examination.
- 4. Perform and record vital signs.
- 5. Perform and record oximetry.
- 6. Perform and record spirometry.
- 7. Perform and record post-bronchodilator spirometry.
- 8. Collect any unused study drug.
- 9. Review diary card.
- 10. Obtain a CT scan of the thorax.
- 11. Collect induced sputum.
- 12. Schedule participant for Visit 6 in 14 days.

9.6 Visit 6 (Day 28)

- 1. Record changes to concomitant medications.
- 2. Perform and record vital signs.
- 3. Perform and record oximetry.
- 4. Perform and record spirometry.
- 5. Perform and record post-bronchodilator spirometry.
- 6. Schedule participant for Visit 7 in 14 days.

9.7 Visit 7 (Day 42)

- 1. Record changes to concomitant medications.
- 2. Perform abbreviated physical examination.
- 3. Perform and record vital signs.
- 4. Perform and record oximetry.
- 5. Perform and record urine pregnancy test.
- 6. Perform and record spirometry.
- 7. Perform and record post-bronchodilator spirometry.
- 8. Provide education on use of personal nebulizer and administration of study medication.
- 9. Dispense study drug and initiate study diary.
- 10. Perform RN/MD supervised administration of first dose of nebulized study drug.
- 11. Obtain a CT scan of the thorax.
- 12. Collect induced sputum.
- 13. Schedule participant for Visit 8 in 7 days.

Version #:1.5 Version Date: 8/5/2016 Page 28 of 41

9.8 Visit 8 (Day 47)

- 1. Record any adverse experiences and/or review participant diary for adverse experiences and exclusionary medication use.
- 2. Record changes to concomitant medications.
- 3. Perform abbreviated physical examination.
- 4. Perform and record vital signs.
- 5. Perform and record oximetry.
- 6. Perform and record spirometry.
- 7. Perform and record post-bronchodilator spirometry.
- 8. Collect any unused study drug.
- 9. Review diary card.
- 10. Obtain a CT scan of the thorax.
- 11. Collect induced sputum.

9.9 Early Withdrawal Visit

- 1. Record any Adverse Experiences and/or Review participant diary for adverse experiences and exclusionary medication use.
- 2. Record changes to concomitant medications.
- 3. Perform abbreviated physical examination.
- 4. Perform and record vital signs.
- 5. Perform and record oximetry.
- 6. Perform and record urine pregnancy test.
- 7. Perform and record spirometry.
- 8. Perform and record post-bronchodilator spirometry.
- 9. Collect any unused study drug.
- 10. Review dairy card.

10 ADVERSE EXPERIENCE REPORTING AND DOCUMENTATION

10.1 Adverse Events

An adverse event (AE) is any untoward medical occurrence in a clinical investigation of a patient administered a pharmaceutical product and that does not necessarily have a causal relationship with the treatment. An AE is therefore any unfavorable and unintended sign (including an abnormal laboratory finding), symptom or disease temporally associated with the administration of an investigational product, whether or not related to that investigational product. An unexpected AE is one of a type not identified in nature, severity, or frequency in the current Investigator's Brochure or of greater severity or frequency than expected based on the information in the Investigator's Brochure.

The Investigator will probe, via discussion with the participant, for the occurrence of AEs during each participant visit and record the information in the site's source documents. Adverse events will be recorded in the participant CRF. Adverse events will be described

Version #:1.5 Version Date: 8/5/2016 Page 29 of 41

by duration (start and stop dates and times), severity, outcome, treatment and relation to study drug, or if unrelated, the cause.

AE Severity

The National Cancer Institute's Common Terminology Criteria for Adverse Events (CTCAE) Version 3.0 should be used to assess and grade AE severity, including laboratory abnormalities judged to be clinically significant. The modified criteria can be found in the study manual. If the experience is not covered in the modified criteria, the guidelines shown in Table below should be used to grade severity. It should be pointed out that the term "severe" is a measure of intensity and that a severe AE is not necessarily serious.

Table 3. AE Severity Grading

Severity (Toxicity Grade)	Description
Mild (1)	Transient or mild discomfort; no limitation in activity; no medical intervention or therapy required. The participant may be aware of the sign or symptom but tolerates it reasonably well.
Moderate (2)	Mild to moderate limitation in activity, no or minimal medical intervention/therapy required.
Severe (3)	Marked limitation in activity, medical intervention/therapy required, hospitalizations possible.
Life-threatening (4)	The participant is at risk of death due to the adverse experience as it occurred. This does not refer to an experience that hypothetically might have caused death if it were more severe.

AE Relationship to Study Drug

The relationship of an AE to the study drug should be assessed using the following the guidelines in Table .

Table 4. AE Relationship to Study Drug

Relationship to Drug	Comment				
Definitely	Previously known toxicity of agent; or an event that follows a reasonable temporal sequence from administration of the drug; that follows a known or expected response pattern to the suspected drug; that is confirmed by stopping or reducing the dosage of the drug; and that is not explained by any other reasonable hypothesis.				
Probably	An event that follows a reasonable temporal sequence from administration of the drug; that follows a known or expected response pattern to the suspected drug; that is confirmed by stopping or reducing the dosage of the drug; and that is unlikely to be explained by the known characteristics of the participant's clinical state or by other interventions.				
Possibly	An event that follows a reasonable temporal sequence from administration of the drug; that follows a known or expected response pattern to that suspected drug; but that could readily have been produced by a number of other factors.				

Version #:1.5 Version Date: 8/5/2016 Page 30 of 41

Unrelated	An event that can be determined with certainty to have no relationship to the study
	drug.

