5.3 Safety Evaluations

All participants will have their first dose of treatment or normal saline administered in the clinical laboratory environment under the supervision of a study nurse or study clinician. Participants will receive instruction on nebulizer use utilizing a teach-back method to ensure comprehension. Participants who are unable to successfully teach back nebulizer setup or drug self-administration will be excluded from continued participation.

Additionally, while acute anaphylactoid reactions have only been observed in the setting of IV administered NAC, each participant will be observed for 30 minutes following initiation of each new study period by a study nurse or study clinician.

All participants will be asked to complete a log of study drug administration, concomitant medications, and any subjective side effects (appendix A). Additionally, participants will have access via pager to a study nurse or clinician 24 hours a day, 7 days a week.

Interim safety evaluations will be triggered if anticipated adverse events exceed frequencies documented in the literature, unanticipated adverse events occur, or rare but serious adverse events occur. Definitions of these terms and details of our safety evaluation plan are described in section 14.

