14.4 Analysis of Secondary Endpoints

As a secondary outcome, we will include an analysis that examines the change associated with the 7-day treatment with 0.9% saline. Our secondary analysis is to determine the characteristics of participants that respond to NAC. We will classify participants in four groups based on their post-bronchodilator FEV1 in response to NAC. FEV1 of 0-4% change will define non-responders and FEV1 of 5-9%, 10-14%, or > 15% will define the 3 categories of responders. We will examine NAC responders and non-responders to determine if baseline CT mucus scores, lung function measures, or sputum G' measures predict treatment response. We will construct ROC curves to determine the CT score that predicts NAC response thereby identifying a CT biomarker for future thiol saccharide trials. In addition, we will examine how the CT mucus score changes with NAC treatment using a subset of the participants following second period treatment. Finding a decrease in CT score in the 20% NAC group compared to the placebo group will provide support for

 our hypothesis that NAC improves lung function by decreasing intraluminal mucus. Other analyses will be to examine the effects of treatment on sputum elasticity (G').

Safety and tolerability data will be summarized by treatment group.

Adverse event rates will be coded by body system and MedDra classification term. Adverse events will be tabulated by treatment group and will include the number of patients for whom the event occurred, the rate of occurrence, and the severity and relationship to study drug.

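### Table 4's causality categories overlap for known NAC effects and leave novel events without a category, so the planned relationship-to-drug breakdown is unreliable

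*Combined protocol and SAP*

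**What the plan says.** Section 10.1 requires the relationship of each adverse event to study drug to be assessed with the guidelines in Table 4, which has four rows.

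- **Definitely**: "Previously known toxicity of agent; or an event that follows a reasonable temporal sequence from administration of the drug", continuing with a known or expected pattern, confirmation by stopping or reducing the drug, and no other reasonable explanation.
- **Probably**: reasonable timing, "that follows a known or expected response pattern to the suspected drug; that is confirmed by stopping or reducing the dosage of the drug", and unlikely to be explained by the participant's clinical state or other interventions.
- **Possibly**: reasonable timing, and an event "that follows a known or expected response pattern to that suspected drug; but that could readily" have arisen from other factors.
- **Unrelated**: "An event that can be determined with certainty to have no relationship to the study" drug.

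Section 14.4 tabulates adverse events by treatment group. The table is to give the number of patients affected, "the rate of occurrence, and the severity and relationship to study drug". In the available text this is the only planned output that uses the Table 4 code.

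Section 2.1 names ten effects of inhaled NAC: nausea, vomiting, stomatitis, cough, hemoptysis, rhinorrhea, fever, chills, raised intracranial pressure and somnolence.

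**The concern.** A causality scale should give each event exactly one code. This one appears to fail in two ways.

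First, the word *or* near the start of the Definitely row makes known toxicity sufficient. Timing, response to stopping and alternative cause then count only for effects not already known. Several of the ten effects have obvious other causes in this trial. Section 8.1.9 lists shortness of breath or cough as a likely effect of spirometry (>10%). Section 8.1.12 lists coughing among the likely effects of sputum induction (>25%). Assessors are blinded (section 7.2), so a cough in the saline period would be coded Definitely just as one in the NAC period would.

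Second, every category of relatedness, apart from that first clause, asks for a known or expected pattern, and Unrelated asks for certainty. A new reaction of uncertain cause, for which a causality judgement is most useful, has no code.

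At stake is whether the relationship column in the safety table can be interpreted. With about 30 participants, a few arbitrary codes would visibly change it.

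**Working it through.** The plan gives no figure on this point to reproduce. The check is one of logic, with a small illustration of scale.

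**Step 1. Table 4 as conditions.** K = known toxicity; T = reasonable timing; P = known or expected pattern; D = confirmed by stopping or reducing the drug; N = no other reasonable explanation; U = other explanations unlikely; F = other factors could readily have produced it; C = certainly no relationship.

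- Definitely = K or (T and P and D and N)
- Probably = T and P and D and U
- Possibly = T and P and F
- Unrelated = C

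**Step 2. Admissible combinations.** Four constraints are assumed: N implies U; F excludes N and U; K implies P; C excludes N and U. The pair (K, P) can take 3 values, (T, D) 4 values and (N, U, F, C) 6 values, of which 4 have C false. The total is 3 × 4 × 6 = 72.

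**Step 3. Novel events.** Set K, P and C all false. This leaves 1 × 4 × 4 = 16 combinations. Without K or P, none of the first three rows can be met; without C, the fourth cannot. All 16 have no category.

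**Step 4. Test cases.**

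| Event | Category as written |
|---|---|
| Known effect, implausible timing, not confirmed by stopping, other causes ready | Definitely |
| Known effect, good timing, not confirmed by stopping, other causes ready | Definitely and Possibly |
| Known effect, certainly not caused by the drug | Definitely and Unrelated |
| Novel effect, good timing, confirmed by stopping, no other cause | none |

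**Step 5. Scale at n = 30.** This assumes that the rates quoted in the protocol apply per participant, which it does not state.

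- Nausea at 2–7%: 30 × 0.02 = 0.6 to 30 × 0.07 = 2.1 participants.
- Vomiting at 9–12%: 30 × 0.09 = 2.7 to 30 × 0.12 = 3.6 participants.
- Spirometry symptoms at >10%: more than 30 × 0.10 = 3 participants per round.
- Sputum induction symptoms at >25%: more than 30 × 0.25 = 7.5 participants per round, if all 30 undergo it.

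The nausea and vomiting cases would be Definitely by name alone. The procedure rates cover groups of symptoms, of which cough is only one. Coughs among them would be Definitely too if recorded as adverse events.

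**The case against.** The strongest defence is that little depends on this column. That is largely right, and it limits the point.

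- **Unexpected events.** A reader might infer that detection of unexpected events is broken. The documents do not support this. Section 10.1 sets an unexpected AE against the Investigator's Brochure ("An unexpected AE is one of a type not identified in nature, severity, or frequency in the current" Brochure) and uses no causality term. The interim trigger in section 5.3 is that "unanticipated adverse events occur, or rare but serious adverse events occur", again with no relatedness condition. Sections 10.2.1 and 16.2 have SAEs documented and reported whatever their cause. Part of the text after section 10.2.1 was not available, so nothing is inferred about other reporting rules.
- **Tolerability.** A reader might infer that the tolerability conclusion for NAC rests on Table 4. It does not. Sections 5.2 and 14.4 describe frequencies without restriction to related events, and every participant is due a blinded saline period for comparison. No test, endpoint or stopping rule in the available text uses the code.
- **Forced coding.** It is tempting to say that a novel reaction must be called Unrelated. Table 4 does not allow that without certainty. What follows is inconsistent coding between assessors.
- **All asthma symptoms.** Nor does Definitely become an all-cause count of asthma symptoms. Of the four symptoms with their own diary column in Appendix A, only cough is on the section 2.1 list. Section 7.4.1 mentions transient lung irritation from NAC, which leaves the status of the other three unclear.
- **Guidelines, or a slip.** Table 4 is offered as guidance, and the *or* may be a drafting error. But section 10.1 directs assessors to use it, and the gap for novel events remains even if the *or* is corrected.

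What stands after all this is the overlap, the gap, and their effect on the relationship breakdown.

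**Conclusion.** Wrong as written, with a narrow reach. On a literal reading, all ten effects in section 2.1 qualify as Definitely on the first clause alone and can meet Possibly or Unrelated as well. Every novel event that is not certainly unrelated (16 of 16 admissible combinations) has no category. The relationship column in section 14.4 is therefore unreliable for known effects and undefined for novel ones.

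The all-AE counts and rates by treatment group, the NAC-versus-saline comparison built on them, the unexpected-AE definition, the interim trigger, SAE reporting and the primary endpoint are untouched. The conclusion rests on the wording of Table 4 and the constraints in step 2. The counts at n = 30 are illustrative only. The point is worth correcting because the plan commits to this output and the correction costs almost nothing.

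**What to change.** Reword Table 4:

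1. **Definitely**: delete the opening known-toxicity clause together with its *or*, so that timing, response to stopping and alternative cause always apply. Changing *or* to *and* would not do, since it would make prior knowledge of the toxicity compulsory.
2. **Possibly**: plausible timing where a drug cause cannot be excluded, whether or not the pattern is known and whether or not another cause is present, for events that do not meet Definitely or Probably. Merely dropping the pattern requirement is not enough: a novel, well-timed event confirmed by stopping, with no other cause, would still have no category.
3. **Unrelated**: timing incompatible, or another cause clearly responsible, in place of certainty.

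State that the rows are applied in order and the first one met is used, because an event meeting Definitely would otherwise also meet Probably. The four categories are then mutually exclusive and exhaustive. In the step 4 table, the first case becomes Unrelated if its timing is incompatible, the second Possibly unless another cause is clearly responsible, the third Unrelated and the fourth Possibly.

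The cost is the wording of one table and a note to assessors. The downside is that some more events will be coded Possibly, and a convincing novel reaction can be coded no higher than that.
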